9.4 UNBLINDING

Unblinding is restricted to clinically relevant needs impacting patient safety. It should be used only under circumstances where the knowledge of the treatment is necessary for the proper care of the patient. If the treatment code is broken, the reason and date should be recorded and signed by the investigator. If treatment is discontinued prematurely for any reason other than disease progression the study data centre (Centro Clinical Trials) should be informed immediately. All patients will continue to be followed-up, irrespective of whether they have discontinued treatment prematurely.

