8.5 WITHDRAWAL CRITERIA

Subjects can voluntarily withdraw at any time from the study and follow-up assessments. All data collected up to that point will be retained. Any collected biological specimens will be kept and used for research unless subjects request that these unused samples are destroyed.

A patient's participation in the study may also be discontinued at any time at the discretion of the investigator, and justifiable reasons include Suspected Unexpected Serious Adverse Reactions (SUSAR) or deterioration in the disease activity requiring immunomodulatory treatment but their data until that point will be included in the analysis.

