9.2 RANDOMISATION PRACTICALITIES

All subjects will be randomised after the investigator has verified that they are eligible by the criteria (section 8). Randomisation will be carried out within a web-based system, made available to authorised researchers, by the Clinical Research Organisation (CRO) in charge: *Centro Clinical Trials, [contact] Email: [contact]*

Eligible patients will be randomised to receive immediate vs. delayed treatment with either autologous MSCs or equivalent volume of suspension media at baseline. At 6 months, patients and investigators will continue to be blinded to therapy, but treatments will be reversed (i.e. those who received initial MSCs will receive suspension media and vice versa).

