12.8 MRI PROCEDURES

12.8.1. Outline

All patients will be scanned at one site: the MS Society-funded 3T MRI scanner at the UCL Institute of Neurology. Scans will be acquired at weeks 0, 4, 12, 24, 28, 36 and 48. If drop-out occurs before the study ends, all remaining MRI scans will be obtained, if possible, at the scheduled time-points or if this will not be possible, at an unscheduled visit (exit visit). The MRIs will be analysed by [name] group at the Institute of Neurology but as the data will also contribute to the international collaborative effort, these MRIs will be anonymised and sent to the Medical Image Analysis Centre (MIAC), located in Basel, Switzerland which is being used for analysis of the primary outcomes.

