13.2 SAMPLE SIZE

Up to 23 patients are expected to be enrolled in the clinical trial for evaluation of the primary outcome (safety). Data from this clinical trial and from all other national trials will be pooled together for efficacy evaluation which will be evaluated as a decrease in the number of GEL (co-primary outcome).

A sample size of 160 patients was estimated to give an 80% power at a significance level of 5% to detect a decrease of 50% in the number of GEL counted during the 6 months duration of treatment. This number was estimated assuming that the average number of total GEL on 3 MRI scans (scan at weeks 4, 12 and 24) will be 7.4 (SD=11.4), that is half of the number of total number of GEL counted over 6 monthly scans in the phase 2 study of oral fingolimod for MS [43] .

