16.3 CONSENT

Consent to enter the study must be sought from each participant only after a full explanation has been given, an information leaflet offered and time allowed for consideration. Signed participant consent should be obtained. The right of the participant to refuse to participate without giving reasons must be respected. After the participant has entered the trial the clinician remains free to give alternative treatment to that specified in the protocol at any stage if he/she feels it is in the participant's best interest, but the reasons for doing so should be recorded. In these cases the participants remain within the study for the purposes of follow-up and data analysis. All participants are free to withdraw at any time from the protocol treatment without giving reasons and without prejudicing further treatment.

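### Section 8.5 implies a data cut-off at discontinuation for deterioration, against 16.3 and 12.8.1, so the GEL co-primary can lose later scans because of disease activity

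*Combined protocol and SAP*

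**What the plan says.** Four sections deal with patients who leave treatment or the study early.

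- **8.5 Withdrawal criteria.** The investigator may discontinue participation. One accepted reason is "deterioration in the disease activity requiring immunomodulatory treatment but their data until that point will be included in the analysis".
- **16.3 Consent.** The clinician may give treatment other than that in the protocol, with reasons recorded. "In these cases the participants remain within the study for the purposes of follow-up and data analysis".
- **12.8.1 Outline (MRI).** "If drop-out occurs before the study ends, all remaining MRI scans will be obtained, if possible, at the scheduled time-points", or otherwise at an exit visit.
- **9.4 Unblinding.** "All patients will continue to be followed-up, irrespective of whether they have discontinued treatment prematurely". This concerns stopping treatment, not ending participation.

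Section 8.4 bars disease-modifying therapy during the study. Sections 13.3 and 13.6 take the total GEL over three scans (weeks 4, 12 and 24) and fit an NB regression on treatment group, adjusted for baseline GEL. Section 13 gives no offset for the number of scans obtained, no rule for missing scans, and no rule for scans taken after other treatment has started.

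**The concern.** One patient can fall under two rules. Suppose a patient worsens after the week 4 scan and starts immunomodulatory treatment. Under 8.5 participation may end, with data to that point analysed. Under 16.3 the same patient stays in follow-up and analysis, and under 12.8.1 the week 12 and 24 scans are still sought. Two analysts working from the same protocol could build different co-primary data sets.

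The choice matters because the reason for leaving is tied to the outcome. A patient cut off after week 4 contributes a one-scan total to a model that treats it as a three-scan total. If MSCs reduce lesions, more placebo than MSC patients meet the criterion and more placebo lesions go uncounted, so the ratio moves toward 1. If MSCs increased activity, the same process would hide part of that harm.

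**Working it through.** **1. Inputs.** Section 13.2 gives 160 pooled patients, 80% power, 5% significance, a 50% decrease, and a mean of 7.4 (SD 11.4) for total GEL over three scans. Section 9.2 states no allocation ratio ("Eligible patients will be randomised to receive immediate vs. delayed treatment"), so 1:1 is assumed.

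**2. The plan's own figure.**

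- NB dispersion: k = (11.4² − 7.4) / 7.4² = 122.56 / 54.76 = 2.238.
- n per arm = (1.960 + 0.842)² × [(1/7.4 + k) + (1/3.7 + k)] / (ln 0.5)² = 7.849 × 4.882 / 0.480 = 79.7.
- This rounds up to 80 per arm, or 160 in total. The stated size reproduces (two-sided) and contains no allowance for lost data.

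**3. Effect of cutting data off.** The documents give neither a discontinuation rate nor a numerical trigger, so both are assumed. Counts on three scans are gamma-Poisson, with equal expected counts per scan, a shared patient effect, k = 2.238, a placebo mean of 7.4 and a true ratio of 0.50. After a week 4 or week 12 scan with at least 5 (or 8) GEL, the patient is discontinued with probability 0.3 or 0.5 and later scans are lost.

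Across the four scenarios, 5-15% of placebo and 1-6% of MSC patients are cut off. The two with probability 0.5:

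| Trigger | Cut off, placebo / MSC | Mean observed total, placebo / MSC | Ratio |
|---|---|---|---|
| ≥5 GEL | 15.0% / 6.4% | 5.45 / 3.14 | 0.58 |
| ≥8 GEL | 7.8% / 2.2% | 6.07 / 3.45 | 0.57 |

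In the first row placebo loses 7.4 − 5.45 = 1.95 lesions per patient (26%) and MSC loses 3.7 − 3.14 = 0.56 (15%). That unequal loss moves the ratio. Over all four scenarios, truncated totals give about 0.54-0.58.

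**4. Effect of an offset.** NB regression with a log(scans obtained) offset returns 0.49-0.51 in the same scenarios. This is expected: leaving depends only on counts already observed, and under a shared gamma effect the patient's total and number of scans carry all the information. In trials of 80 per arm (≥5 GEL, probability 0.5), simulated power is 81% with all scans, 68% with truncated totals and no offset, and 80% with the offset.

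**5. Effect of keeping every scan.** If the new treatment did not alter GEL, full follow-up would return 0.50. If it lowers later GEL by an assumed 50-90%, full follow-up gives 0.52-0.57 in the same four scenarios.

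**The case against.** The strongest reply is that 8.5 does not order a cut-off. Its wording can be read as protecting data already collected, and 12.8.1 is the specific rule for MRI, so the two could coexist. A reader might infer that the plan discards later scans; the documents do not say that. What stands is that 8.5 ends participation and implies the cut-off, 16.3 says the opposite for the same event, and section 13 does not decide between them.

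Section 9.4 is also weak evidence of conflict. It concerns stopping treatment, and after the week 0 infusion no study infusion falls before the week 24 scan, which precedes the second infusion. The conflict rests on 8.5 against 16.3 and 12.8.1.

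Three stronger statistical readings are tempting and unsupported:

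- **That an offset cannot repair the bias.** A crude ratio of summed lesions over summed scans stays at 0.52-0.55, but that is not the NB model with an offset, which returns about 0.50 under this mechanism.
- **That continued follow-up alone restores 0.50.** This holds only if the new treatment leaves GEL unchanged.
- **That the loss always falls on placebo, or could create a false benefit.** With no treatment effect and the same trigger in both arms, the ratio stays at about 0.99.

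Finally, a GEL-count trigger is not in 8.5. The nearest figure, at least 5 lesions above baseline in 9.4.1, governs unblinding rather than discontinuation. The sizes are illustrations.

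**Conclusion.** The point holds as an inconsistency with a plausible bias, not as a demonstrated error in the result. If 8.5 is followed, scans are lost because of disease activity, and the planned NB model without an offset moves a true ratio of 0.50 to about 0.54-0.58 under the assumed triggers. The bias is toward no difference if MSCs work; if they worsen activity, it conceals harm.

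It bears mainly on the pooled analysis, where section 13.2 places the efficacy evaluation. This trial expects up to 23 patients, with safety as its primary outcome; by the formula above, 23 patients alone have about 19% power for GEL.

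The size rests on the assumed trigger and discontinuation probability, equal expected counts per scan, and the same rule in both arms. The offset result further requires that leaving depends only on observed counts. It is not guaranteed if clinical findings or knowledge of the allocation drive the decision, and 9.3 leaves the treating team unblinded.

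**What to change.** 1. Reconcile 8.5 with 12.8.1 and 16.3, and align 9.4: discontinuation by the investigator does not end data collection; only withdrawal of consent for follow-up does.
2. In section 13, analyse all scans obtained by randomised group, and add a log(number of scans obtained) offset to the NB model.
3. Record the start date of any new immunomodulatory treatment.
4. State that scans after that date count in the primary analysis (treatment-policy). Add a sensitivity analysis that excludes them and uses the offset.

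The cost is amendment wording and one recorded date; the scans are already scheduled. The downside is that scans taken on other treatment dilute the contrast (0.52-0.57 in the scenarios above, if that treatment lowers later GEL by an assumed 50-90%). The sensitivity analysis addresses this. Because the co-primary is pooled, the same rule should be agreed across the national trials.

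This concerns data retention and analysis only. It sets no clinical rule on when to stop or change treatment.

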9.4.1. Reasons for unblinding

Clinical events: This includes the occurrence of fatal or life-threatening SAE, or any circumstances wherein the judgment of the treating neurologist, blind to the treatment modality, may compromise patient safety or where the patient is unable to provide informed consent to clinically necessary investigations, procedures or treatments as a consequence of the blinding.

MRI findings: Any radiological evidence suggestive of anomalous disease exacerbation or adverse event. This refers to an increase of ≥ 5 number of lesions above the number of lesions on the baseline scan, or the appearance of atypical lesions as assessed by the reviewing radiologist (section 14.1.1). The treating team will be informed as soon as possible.

10. STUDY TREATMENTS

10.1 BONE MARROW HARVEST

Pre sampling checks:

Coagulation studies will be performed at the Week -10 and Week 0 visit (screening and pre-treatment, respectively). In accordance with JACIE (Joint Accreditation Committee International Society for Cellular Therapy – the European Group for Blood & Marrow Transplantation) requirements, participants will be tested at a maximum of 30 days before bone marrow and skin sampling for HIV 1, HIV 2, Hepatitis B, Hepatitis C, HTLV 1, HTLV 2, CMV, and Syphilis. These latter tests will be done at the Week -10 visit.

Bone marrow sampling:

Bone marrow (BM) will be harvested at week -8 according to the Trust policy. The principle is to collect only the BM rich in stroma and early precursors which are contained in the first part of the aspirate. Therefore, the procedure consists of repetitive extractions of 2 ml of BM aliquots. The procedure will require local anaesthesia and intravenous sedation may be required in selected cases. The procedure can be done as an outpatient in the haematology day-care unit. The entire methodology and SOPs have been established and validated in ten MS patients in Cambridge and in 15 patients with GvHD at Hammersmith Hospital.

The bone marrow aspiration will be performed by the registrar in charge of aspirates according to the SOP for mesenchymal stem cell preparation.

10.2 ISOLATION AND EXPANSION OF AUTOLOGOUS MSCS

The Haematology Laboratory (based at Imperial College London), will receive the bone marrow and will act as the manufacturing site for the trial. It will produce the MSCs under the existing GMP license and according to the manufacturing protocol as described in the IMP dossier submitted to the MHRA.

Briefly, MSCs are isolated from bone marrow harvests and ex-vivo expanded in the presence of Modified Eagles Medium supplemented with 5% human platelet lysate according to a Standard Operating Procedure included in the MHRA IMP dossier. The final product is tested to exclude growth of aerobic and anaerobic bacteria and defined as adherent cells positive for CD73, CD90 and CD105 and negative for CD45.

Adequate expansion in culture to obtain sufficient number of MSC to achieve the treatment dose is a prerequisite for continuation in the trial. MSC preparations that have not expanded to confluence (to reach a target of 1-2 million cells/kg body weight) within 52 days from the start of culture will be aborted and the subject will be withdrawn from the study. If the expansion is <1 million cells/kg body weight, then these cells will be stored in the biobank at Imperial College London. Consent for these actions will have been sought at the screening visit.

10.3 RELEASE OF THE MSC PRODUCT FOR CLINICAL USE

MSCs may be released from the laboratory for clinical use if they fulfill the provisions of the advanced therapy medicinal products (ATMP) license described in the dossier approved by the MHRA.

MSC preparations that have not passed the release criteria will be disqualified for trial clinical use and the subject will be withdrawn from the study.

10.4 STUDY TREATMENT INFUSION OF AUTOLOGOUS MSCS OR PLACEBO

At week 0 and at week 24, a single infusion of either ex-vivo expanded autologous MSCs or suspension media will be administered intravenously. For MSCs, we will give a dose of $1-2 \times 10^6$ MSC/Kg recipient body weight (as measured at baseline).

10.5 POST-STUDY TREATMENT INFUSION EVALUATION

Following the study treatment, patients will be monitored for infusion-related toxicity for three hours. Temperature, blood pressure, pulse and oxygen saturation will be measured at baseline and after 15 minutes, 60 minutes and 3 hours. Any toxicity will be treated at the discretion of the attending physician.

10.6 TOXICITY ASSESSMENT

Infusion-related toxicity is defined as any of the following within three hours post-treatment infusion:

- Systolic blood pressure (mmHg) <90 or >180, or >33% decrease or increase from baseline.
- Diastolic blood pressure (mmHg) <50 or >100, or >33% decrease or increase from baseline.
- Heart rate: <60 or >110 or >33% decrease or increase from baseline.
- Body temperature (°C) >38.5 or >1°C increase.
- Any other toxic side effect.

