11.3.1. Non-serious AR/AEs

All such toxicities, whether expected or not, should be recorded in the toxicity section of the relevant case report form and sent to the study coordination centre within one month of the relevant AR/AE.

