13. STATISTICS AND DATA ANALYSIS

13.1 RATIONALE

The main aim of each national trial participating in this international collaborative effort, including the present one, is to assess the feasibility, safety and the toxicity of MSC infusion, as administered within this specific treatment protocol, in active MS. To fulfill this aim, all randomised patients receiving at least one MSCs infusion (or infusion media) will be followed for at least two years after the last study drug administration. All adverse events will be recorded and compared in the two treatment groups. Comparative analyses of the incidence of new GEL at MRI acquired on conventional 1.5 T MRI scans over 24 weeks will be conducted as well, to provide preliminary data on the activity of the experimental treatment. However, the main analyses of safety, toxicity and activity will be those on the entire data set obtained by pooling the results of all national trials, for an expected total of 160 randomised patients.

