14.1.6. Mesenchymal stem cell infusion

During the infusion, allergic reactions can occur - these include transient fever and headaches. Potentially more significant allergic reactions can occur but are very rare.

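### Section 10.6 can count an unchanged pulse or blood pressure as infusion toxicity, and its counting window leaves out the infusion itself (minor)

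*Combined protocol and SAP*

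**What the plan says.** Section 10.6 sets the time frame and the criteria: "Infusion-related toxicity is defined as any of the following within three hours post-treatment infusion". The heart-rate criterion is "Heart rate: <60 or >110 or >33% decrease or increase from baseline". Systolic pressure (below 90 or above 180) and diastolic pressure (below 50 or above 100) follow the same pattern: two absolute limits and a relative change of more than 33%, joined by the word or. The list ends with a catch-all item for other toxic effects, which falls under the same time frame.

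Section 10.5 describes the observation: "Following the study treatment, patients will be monitored for infusion-related toxicity for three hours". The readings are specified: "Temperature, blood pressure, pulse and oxygen saturation will be measured at baseline and after 15 minutes, 60 minutes and 3 hours". A pre-infusion value therefore exists for every vital sign in the definition. No reading during the infusion is listed.

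Section 14.1.6 describes when reactions to the cells are expected: "During the infusion, allergic reactions can occur - these include transient fever and headaches".

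Section 13.1 says that the main aim of each national trial "is to assess the feasibility, safety and the toxicity of MSC infusion, as administered within this specific treatment protocol, in active MS", and it names toxicity among the main pooled analyses. It also says: "All adverse events will be recorded and compared in the two treatment groups". Section 11.3.1, on non-serious reactions and events, says: "All such toxicities, whether expected or not, should be recorded in the toxicity section of the relevant case report form".

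**The concern.** The definition can misclassify in two directions.

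- **Over-count.** The absolute limits do not refer to the pre-infusion value, although section 10.5 records it. A patient whose resting pulse is already below 60 meets the definition after either infusion with no change at all. These cases carry no information about treatment. They arise in both arms alike, so they mask a difference rather than create one. For a safety aim, that is the unhelpful direction.
- **Under-count.** The period in which section 14.1.6 places fever and headache lies outside the period that section 10.6 counts. A reaction that begins and resolves while the infusion is running meets no criterion, and the catch-all item does not bring it back in.

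At stake is the between-group count of infusion-related toxicity, which section 13.1 makes part of the aim and of the pooled analyses.

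**Working it through.** The plan states no figure for infusion toxicity, so there is none to reproduce. The check applies the rule as written and then asks how many patients it could affect.

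**1. The heart-rate rule on example values.** With b the pre-infusion rate and h a later rate, a case is h < 60, or h > 110, or h > 1.33b, or h < 0.67b.

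| Before | After | Change | Counted? |
|---|---|---|---|
| 58 | 58 | 0% | yes |
| 55 | 57 | +3.6% | yes |
| 62 | 59 | −4.8% | yes |
| 70 | 70 | 0% | no |
| 90 | 61 | −32.2% | no |

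A patient at 58 avoids being counted only if every later reading lies between 60 and 77 (58 × 1.33 = 77.1). For baselines from 60 up to 60/0.67 = 89.6, a falling pulse crosses 60 before it has fallen by 33%. The relative criterion for a fall therefore matters only above about 90.

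**2. How many patients start below 60?** The documents give no heart-rate distribution. Assumption: normal, mean 65 to 80, SD 8 to 12 beats/min. Share = Φ((60 − mean)/SD), applied to the up to 23 patients of section 13.2.

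- Mean 80, SD 8: Φ(−2.50) = 0.6%; 23 × 0.006 = 0.1 patients.
- Mean 70, SD 10: Φ(−1.00) = 15.9%; 23 × 0.159 = 3.6 patients.
- Mean 65, SD 12: Φ(−0.42) = 33.8%; 23 × 0.338 = 7.8 patients.

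This covers the lower heart-rate limit only. The blood-pressure limits could add to it.

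**3. What this does to a between-group difference.** Let a share f of patients in both arms be counted regardless of treatment, independently of true toxicity t. Then the observed rate = t + (1 − t)f, and the observed difference = (1 − f) × the true difference. Over the range in step 2, 99.4% (f = 0.006) down to 66.2% (f = 0.338) of a true difference remains.

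Illustration, with true rates of 10% v 40% assumed:

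- f = 0.16: 0.10 + 0.90 × 0.16 = 24.4% v 0.40 + 0.60 × 0.16 = 49.6%. The difference is 25 points instead of 30.
- f = 0.31: 37.9% v 58.6%. The difference is 21 points.

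A two-group comparison with 12 per arm would have power of 39% with no background, 24% at f = 0.16 and 17% at f = 0.31. The plan specifies no such test; the figures show only direction and order of size.

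**4. The window.** Section 14.1.6 places the named reactions during the infusion. Section 10.5 begins monitoring after treatment, and section 10.6 counts the three hours after it. A reaction still present after the infusion is counted; one that has settled by then is not. The infusion's duration is not stated, so this gap cannot be sized.

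**The case against.** The strongest reply is that neither error need reach the primary safety comparison, and much of this reply stands.

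- A reader might infer that the adverse-event comparison in section 13.3 is itself contaminated by unchanged vital signs. The documents do not support that. Section 11.3.1 sends adverse events to the toxicity section of the CRF; it does not say that crossing a 10.6 limit creates an adverse event. Section 11.1 requires an untoward occurrence or an unfavourable sign, and an unchanged pulse of 57 need not be either.
- A reader might infer that reactions during the infusion are lost from the safety data. They are not. Sections 11.3 and 13.1 require all adverse events to be recorded, with no post-infusion window, and events are recorded at the Week 0 and Week 24 visits. Only the toxicity label is missed.
- Sections 13.3 to 13.6 specify no test or rate for 10.6 cases, so any diluted ratio describes an analysis that the reviewer has constructed.
- The size rests on assumptions, and the low end of the range is immaterial.
- Section 10.5 does not say from which moment 15 minutes is counted, so some readings might fall within the infusion.

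A further objection concerns the remedy. Switching an absolute limit off whenever the pre-infusion value already lies outside it would hide real deterioration. A pulse falling from 57 to 40 is −29.8% and a systolic pressure falling from 88 to 62 is −29.5%. Both count now, and neither exceeds 33%. That objection is right, and the fix below avoids the problem.

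What remains is that the plan's only definition of a quantity named in its main aim labels no change as toxicity, and excludes the period in which its own risk section expects reactions.

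**Conclusion.** The point holds as a minor defect in an outcome definition. On the literal text, section 10.6 counts values that the infusion did not alter and omits reactions confined to the infusion. The first adds background to both arms and shrinks any MSC v placebo difference in the toxicity count; the second removes some true cases from that count.

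The size is not derivable from the documents. For heart rate below 60 alone it runs from practically nobody to about 8 of 23 patients, on assumed normal distributions and on the assumption that a low pulse stays low after the infusion. It would be too strong to say that the primary adverse-event comparison is biased, or to attach one dilution ratio to the trial.

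**What to change.** Reconcile sections 10.5, 10.6 and 14.1.6, for outcome counting only. The existing limits, the monitoring and the care given stay as they are; which limits are clinically right is for the sponsor.

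1. Define baseline in 10.5 and 10.6 as the reading taken before each infusion, so that the Week 24 infusion has its own reference.
2. For the between-group toxicity count, code an out-of-limit value as infusion-related only when it is treatment-emergent: absent before the infusion, or worse than the pre-infusion value in the same direction. Under this rule 58 to 58 and 55 to 57 are not counted, while 57 to 40 and 88 to 62 still are.
3. State in advance what counts as worse. With three later readings, ordinary variation will often put one of them a beat below the first.
4. List pre-existing out-of-limit values separately.
5. Open the counting window at the start of the infusion and keep its present end, so that reactions noted during the infusion are counted.
6. Say whether a 10.6 case is also entered as an adverse event.

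The cost is minor protocol and CRF wording; the pre-infusion values are already collected. Two limits remain. Section 10.5 schedules no reading during the infusion, so the vital-sign criteria in that period rest on whatever staff happen to note. A small chance crossing such as 62 to 59 is new and would still be counted.
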